**Spray in other nostril**  
Place the tip just **inside the other nostril** and with a single motion, depress plunger as **rapidly as possible** to deliver remaining vaccine.

Any unused product will be disposed of in accordance with local requirements for medical waste.

[figure not shown]
## 5.5 DISPENSING AND PRODUCT ACCOUNTABILITY

Fluenz Tetra (quadrivalent LAIV) is approved by the European Medicines Agency and distribution and administration to selected children will take place during the influenza season 2016-17. Provision of doses of vaccine will be through the Department of Health vaccine supply network as part of the national immunisation programme, with no additional requirements (e.g. cold chain monitoring) beyond that provided by the normal UK vaccine supply system. Vaccine will be delivered via existing systems to on-site pharmacists at study sites (all NHS hospitals). Doses will then be released according to local procedure, using existing hospital pharmacy systems and logging (rather than CTIMP-specific documentation).

The application for a clinical trials authority will include an exemption for study specific labelling.

**6 STUDY VISITS, PROCEDURES SCHEDULE and Patient Flow Diagram**

The study schedule is summarised in the following flow chart and table:

	Visit 1	24 hours later	72 hours later	6-7 days later	Follow-up 4 weeks later
Written Informed Consent (parent/ guardian)	X				
Written assent (child)	X				
Medical assessment	X				
Asthma control/symptom questionnaire: 
 
• Age 2-4 years: TRACK score (Appendix 1)
 
• Age 5-11 years: C-ACT score (Appendix 2a)
 
• Age 12+ years: ACT score (Appendix 2b)
 
	X				X
Vaccine administration followed by 20 mins observation	X				
Nasal swab at home		X	X	X	
Delayed effects telephone questionnaire at 72hrs			X		
Asthma assessment 4 weeks post LAIV					X
2 nd dose in children <9 years who meet DoH criteria (see 6.1.2)					X

## 6.1 STUDY PROCEDURES

Following consent (see 6.1.2), subjects will be assessed for suitability for vaccine administration. Baseline observations (temperature, heart rate, respiratory rate, oxygen saturations in air and lung function) will be documented on the paper CRF. Asthma control will be assessed as per section 8.1.3.

LAIV will be administered according to the SmPC (see section 5.4) and the child observed for 20 minutes afterwards to confirm no acute adverse event. The observation time will be extended if there is any clinical concern. Vaccine will be administered in a clinical area where facilities exist to manage any adverse reaction, should this occur. Additional surveillance and monitoring will be performed in participants at the Royal Brompton Hospital site (see section 8.6).

Following vaccination, the CRF will be completed and patient details entered on to a secure encrypted server run by Public Health England, confirming vaccine administration and providing the required contact details for follow-up.

---

### 6.1.1 POST VACCINATION SCHEDULE

Parents will be asked to take up to 3 nasal swabs from their child/young person at home, in the week following vaccination. The nasal swab, which looks like a large cotton bud, will be passed into the nostril and moved around for a minute. The exact timing of these will be confirmed prior to study commencement, once international efforts to assess vaccine shedding have been reported. However, it is likely these will be at 24 and 72 hours, and at 6-7 days following vaccination. Parents will be provided with three test kits, full instructions and Royal-Mail approved kits (for Category B specimens) will be provided for each child, along with postage-paid envelopes for posting back to PHE through the normal post network.

Parents will be shown the process by their study nurse at the vaccination visit. The swab may be collected up to 24 hours after the stated time.

From 72 hours after LAIV (and up to 7 days later, to allow for weekends), families will be contacted to document any potential adverse events which have occurred since vaccination. This will be done by telephone contact by staff at the study site. A guide for this telephone call is found in Appendix 5. Families will be reminded about the nasal swab at this time.

One month later, families will receive an email invite from Public Health England to complete a brief online questionnaire to assess asthma control. Where families do not have access to email, this can be completed through telephone contact by staff at the local study site (as per the 72 hour follow-up, using the telephone guide in Appendix 6).

---

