### 3.1.2. SECONDARY STUDY OUTCOMES

1. Incidence of adverse events (AE) and serious adverse events (SAEs) in children receiving LAIV:
  - AEs occurring up to 72 hours after LAIV.
  - SAEs unrelated to asthma symptoms with onset up to 72 hours after LAIV
  - Incidence of a 'significant exacerbation' in asthma, defined as:
    - i. At least 3 day course of oral steroids following an unscheduled contact with a healthcare professional; OR
    - ii. Unscheduled visit to an Emergency department or admission to hospital for treatment of asthma symptoms, requiring systemic corticosteroids
2. Incidence and extent of viral shedding in children and young people receiving LAIV during the 2016/17 influenza season, using quantitative analysis of consecutive nasal swabs obtained up to 10 days following LAIV. These data will be correlated with the incidence of adverse events related to asthma over the same time period.

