Medical judgement should be exercised in deciding whether an AE/AR is serious in other situations. Important AE/ARs that are not immediately life-threatening or do not result in death or hospitalisation but may jeopardise the subject or may require intervention to prevent one of the other outcomes listed in the definition above, should also be considered serious.

**Suspected Unexpected Serious Adverse Reaction (SUSAR):** any suspected adverse reaction related to an IMP that is both unexpected and serious.

**Any symptoms requiring treatment for anaphylaxis** (adrenaline, steroids, salbutamol) **will be classified as a SERIOUS ADVERSE REACTION** and must be documented on both the CRF as well as through completion of a SAE form. The investigator should also make a notification to the MHRA should also be made through the yellow card scheme (<https://yellowcard.mhra.gov.uk/>).

For the purpose of this study, SARs and SAEs not related to asthma/wheezing will only be collected where onset is within 72 hours of vaccine administration. Those relating to respiratory symptoms will be collected up to one month after LAIV at visit 1.

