#### 8.1.3 ASTHMA CONTROL ASSESSMENT PRE AND 4 WEEKS POST VACCINATION

Participants' families will be asked to complete a questionnaire to determine their child's asthma symptoms and control, using a validated tool at visit 1:

- In children age 2-4 years: TRACK questionnaire (Appendix 1)
- In children age 5-11 years: C-ACT questionnaire (Appendix 2a)
- In children age 12+ years: ACT questionnaire (Appendix 2b)

As part of the CRF, the questions on the Asthma Control Questionnaire (ACQ, Appendix 3) will also be completed. While the (C-)ACT and TRACK questionnaires assess asthma symptoms over the preceding 4 weeks, the ACQ assesses symptoms and control over the preceding 7 days and also includes lung function; the ACQ may therefore be more representative of asthma control at the time of vaccination. The (C-)ACT will be completed first, before the ACQ.

Families will be asked to complete a further questionnaire 4 weeks after vaccination. In general, this will be done using an online questionnaire. Families will be asked at their first

visit as to whether they prefer to be contacted by telephone by the study team, or receive an email request with a link to a secure, online survey. Either way, the survey will take 2-3 minutes to complete. A guide for the telephone call is provided in Appendix 6. These data will be recorded on a CRF.

If the family fails to respond to the email request, the local study team will attempt to contact the family by telephone. If, after three attempts (on three separate days), the local study team is unable to contact the family, the child will be deemed lost to follow up and this will be documented on the CRF, which will then be closed.

At the Royal Brompton, participants will be invited to return to hospital for the 4 week follow-up (which will, in general, coincide with a routine clinic follow-up appointment). The follow-up questionnaires will be completed at this visit, along with some further repeat assessments (section 8.3).

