**Guide to telephone interview:**

1. Confirm interviewee's identity

2. Introduce yourself:

*"I am <name> from the SNIFFLE-4 Study. Your child <participant's name> had the 'flu vaccine with us one month ago, and we arranged to speak to find out if you had needed to do anything different with his asthma/wheezing"*

3. Complete appropriate TRACK / C-ACT / ACT Questionnaire over the telephone

(see separate questionnaires)

4. Finally, ask the following questions:

*Since the vaccine,*

*i) Have you had to take <participant's name> to see a Doctor because of his/her breathing?*

*ii) (If YES) – did you have to take them to hospital?*

*iii) (If YES) – did <participant's name> have to stay in hospital overnight?*

*iv) Did <participant's name> have to start any medicines, like an oral steroid? If so, for how long?*

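### The plan does not show that families answering the week-4 follow-up online, or at the Royal Brompton visit, are asked about steroid courses and hospital care since vaccination

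*Combined protocol and SAP*

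**What the plan says.** Section 3.1.2 lists as a secondary outcome "Incidence of a 'significant exacerbation' in asthma, defined as" by an oral steroid course of minimum length after unscheduled contact, or by emergency or hospital care needing systemic steroids. For serious events, section 7.1 adds: "Those relating to respiratory symptoms will be collected up to one month after LAIV at visit 1".

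After the telephone call at day 3 to 7 (sections 6.1.1 and 8.2), the only further planned contact about the child's health is at week 4. Section 6.1.1 describes it as an email contact: "families will receive an email invite from Public Health England to complete a brief online questionnaire to assess asthma control". Section 8.1.3 confirms the default: "In general, this will be done using an online questionnaire". The telephone is for families without email ("Where families do not have access to email, this can be completed through telephone contact by staff at the local study site"), families who state a preference for it at visit 1, and non-responders ("If the family fails to respond to the email request, the local study team will attempt to contact the family by telephone"). Royal Brompton families are invited to a hospital visit, where they complete the follow-up questionnaires and the section 8.3 assessments.

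The event questions are in the telephone guides. In Appendix 6, item 3 is the TRACK, C-ACT or ACT. Item 4 is separate, opens with "Finally, ask the following questions", and begins: "Have you had to take <participant's name> to see a Doctor because of his/her breathing". It goes on to hospital attendance, overnight stay and oral steroids with duration. Appendix 5 asks similar questions at the early call.

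Section 9.3 analyses everyone who has one or more safety measurements. It estimates exacerbation incidence with a 95% confidence interval, compares it with historical rates by Fisher's exact test, and uses exacerbation as the target of a ROC analysis.

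**The concern.** A significant exacerbation can be counted only if someone asks about steroid courses and hospital care, or if the site learns of them another way. As described, the default week-4 contact is a control questionnaire, and the questions that define the outcome belong to the fallback route.

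If that is how the study runs, ascertainment depends on how the family replied. A child with a steroid course on day 15 is a case if the family was telephoned and may be a non-case if it replied online. Because the analysis set requires only one safety measurement, the early call alone can put that child in the denominator as event-free for the month. The error runs towards apparent safety in the incidence and in the historical comparison, and it feeds missed cases into the ROC analysis. Section 1.3 says the study is meant to inform UK guidance on this vaccine.

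There is also a reporting step to settle. Online replies go to Public Health England, while the 24-hour SAE rule in section 7.1.1 runs from the site team's awareness. The plan does not describe how a positive online answer would reach the site.

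**Working it through.** **1. Could the control scores supply the outcome?**
- C-ACT (Appendix 2a) and ACT (Appendix 2b) have no item on oral steroids or hospital care.
- TRACK (Appendix 1, ages 2-4) asks how often oral steroids were needed over 12 months. It gives no date relative to vaccination and no course length. A change from baseline to week 4 mixes new courses with old ones leaving the 12-month window.

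So none of the three can identify a post-vaccine significant exacerbation.

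**2. The plan's own figure.** Section 9.2 gives an upper 95% limit of 0.92% for 0/400. The exact two-sided limit is 1 - 0.025^(1/400) = 0.918%, which agrees. For 4/400 the exact interval is 0.273% to 2.540%, so the stated upper limit of 2.54% also agrees. The stated lower limit of 0.027% does not; it looks like a decimal slip and has no bearing on this point.

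**3. Share of the window not asked about.** Section 3.1.2 gives no explicit window for exacerbation. I take 28 days, from the four-week comparison in section 2.2 and the one-month collection in section 7.1. If the online form carries only the control score, an online responder is asked about events only up to the early call:
- call on day 3: (28 - 3)/28 = 25/28 = 89% not asked about
- call on day 7: (28 - 7)/28 = 21/28 = 75% not asked about

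**4. Effect on the zero-event limit.** Let s be the share replying online and d the day of the early call. With a constant event rate, no passive reporting and event risk unrelated to reply route, the share of events asked about is c = 1 - s × (28 - d)/28. Zero recorded events in 400 is then compatible with a true rate up to 0.918%/c. The documents do not give s, so three values are shown.

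| Assumed online share | c (call on day 3 to day 7) | True rate compatible with 0/400 |
|---|---|---|
| 50% | 0.554 to 0.625 | 1.7% to 1.5% |
| 70% | 0.375 to 0.475 | 2.4% to 1.9% |
| 90% | 0.196 to 0.325 | 4.7% to 2.8% |

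For example, at 70% and day 3, c = 1 - 0.70 × 25/28 = 0.375 and 0.918%/0.375 = 2.4%.

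**5. The other end of the range.** If the online form already carries item 4, all 28 days are asked about for every responder, c = 1, and 0.92% stands apart from ordinary loss to follow-up.

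**The case against.** The strongest reply is that the online form is not in the documents and may mirror Appendix 6. Section 6.1.1 speaks of completing the same thing by telephone using the Appendix 6 guide. Section 8.1.3 gives one duration, 2-3 minutes, for the survey by either mode, and Appendix 6 gives the same duration for the whole call, item 4 included. The schedule in section 6 has a week-4 asthma assessment row separate from the questionnaire row. All this makes a single instrument in two modes plausible. None of it says that the online form or the Royal Brompton visit carries item 4, and the schedule row is not defined. A reader might infer that events after the early call definitely go unasked online. The documents do not support that; they support only that the questions are not shown to be asked.

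It is also fair that sites have other ways of learning about events. Participants are under the care of participating sites (section 4.1), investigators must record adverse events throughout (section 7.1.1), and Royal Brompton families attend in person. A reader might infer that a site would hear of an event only by chance, which goes too far. These channels are real and would shrink the figures above. They are not systematic, though, and a short steroid course prescribed elsewhere is the kind of event they can miss.

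A reader might also infer a threat to the hold rules in section 8.6. Those triggers are ventilation in intensive care, death, and repeated or similar SUSARs. An ordinary steroid course or asthma admission is not by itself a trigger, and nothing shows that such extreme events would go unnoticed because of the online form.

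Finally, the primary outcome is collected by every route and is unaffected.

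**Conclusion.** The point stands as a gap in what the plan shows. It is not proof that events will be missed. The questions that define a named secondary safety outcome are specified only for the telephone, which is not the default week-4 route, and the analysis set does not protect against the resulting route-dependent ascertainment.

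The size runs from nothing, if the form already includes item 4, to 75-89% of the window not systematically asked about for online responders. In the second case, 0/400 is compatible with roughly 1.9-2.4% at an assumed 70% online. That range rests on an inferred 28-day window, an assumed online share, a constant event rate and no passive capture, so it is an upper illustration and not an estimate. The direction, towards apparent safety, does not depend on the online share. The point should be settled before follow-up begins, because answers not asked for at week 4 cannot be reliably recovered later.

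**What to change.** - **Sections 6.1.1 and 8.1.3, and Appendix 6:** make the item 4 questions, with event dates and steroid duration, compulsory on every week-4 route: online form, telephone call and Royal Brompton visit. Use the same wording throughout. If the online form already has them, say so and append it.
- **Sections 6.1.1 and 7.1.1:** state that a positive online answer is passed promptly from Public Health England to the site, so that the existing 24-hour SAE rule can operate.
- **Section 9.3:** for four-week exacerbation incidence, use as denominator only children whose week-4 event questions were answered, and report how many were not.

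The cost is a few extra online items, a notification step and some follow-up calls. The reported rate may be less favourable, and the interval widens with the smaller denominator. At the 89% four-week follow-up that section 9.2 quotes from SNIFFLE-2, 400 becomes 0.89 × 400 = 356, and zero events gives an upper limit of 1 - 0.025^(1/356) = 1.03%. No treatment or visit changes.

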### 6.1.2 SECOND DOSE OF LAIV

Children who meet DoH criteria for specified 'clinical risk categories' (Table 1) and are under 9 years of age and have not received prior seasonal influenza vaccination will be offered a second dose of LAIV at least 4 weeks later. We expect very few children to meet this criteria, as most would have received prior influenza vaccination (in SNIFFLE 1, no child would have required a second dose). However, there is a duty of care to our participants and we are therefore including provision for a second dose in this protocol.

Data pertaining to second visits will be collected on a separate CRF, but not used in the primary analysis.

**Table 1: Clinical risk categories requiring a second dose of LAIV in vaccine-naïve children under age 9 yrs:**

Chronic respiratory disease	
 
• Asthma requiring continuous or repeated use of inhaled or systemic steroids or with previous exacerbations requiring hospital admission.
 
• Chronic obstructive pulmonary disease (COPD) including chronic bronchitis and emphysema; bronchiectasis, cystic fibrosis, interstitial lung fibrosis, pneumoconiosis and bronchopulmonary dysplasia (BPD).
 
• Children who have previously been admitted to hospital for lower respiratory tract disease.
 

Chronic heart disease	Congenital heart disease, hypertension with cardiac complications, chronic heart failure.
Chronic kidney disease	Chronic kidney disease at stage 3, 4 or 5, chronic kidney failure, nephrotic syndrome, kidney transplantation.
Chronic liver disease	Cirrhosis, biliary atresia, chronic hepatitis
Chronic neurological disease	Stroke, transient ischaemic attack (TIA). Conditions in which respiratory function may be compromised due to neurological disease (e.g. polio syndrome sufferers). Clinicians should consider on an individual basis the clinical needs of patients including individuals with cerebral palsy, multiple sclerosis and related or similar conditions; or hereditary and degenerative disease of the nervous system or muscles; or severe neurological or severe learning disability.
Diabetes	Type 1 diabetes, type 2 diabetes requiring insulin or oral hypoglycaemic drugs, diet controlled diabetes.
Immunosuppression	
Immunosuppression due to disease or treatment. Patients undergoing chemotherapy leading to immunosuppression. Asplenia or splenic dysfunction. HIV infection at all stages.
 
Individuals treated with or likely to be treated with systemic steroids for more than a month at a dose greater than 20mg prednisolone per day (any age); or for children under 20kg, a dose greater than 1mg per kg per day.
 
It is difficult to define at what level of immunosuppression a patient could be considered to be at a greater risk of the serious consequences of influenza and should be offered influenza vaccination. This decision is best made on an individual basis and left to the patient’s clinician.
 
Some immunocompromised patients may have a suboptimal immunological response to the vaccine.
 
NB: LAIV is not contraindicated for use in individuals with asymptomatic HIV infection; or individuals who are receiving topical/inhaled corticosteroids or low-dose systemic corticosteroids or those receiving corticosteroids as replacement therapy, e.g. for adrenal insufficiency.

## 6.2 CONSENT

We will endeavour to provide the Patient Information Leaflets prior to visit to hospital, but this may not always be possible. Patients may therefore be consented (according to Good Clinical Practice) without a requirement for a 'cooling-off' period following receipt of the study information leaflets, **where this is specifically requested by the family**. In this case, at least 30 minutes will be allowed for participants and their carers to read the patient information provided and consider the contents.

The reasons for this were highlighted in the PPI discussions during the development of the previous SNIFFLE protocols and include:

- Many families travel significant distances to specialist allergy/respiratory clinics, often requiring the child to miss school and their parents/carers to miss work. In SNIFFLE-1, families frequently requested vaccination at the same time as their routine outpatient appointment, to avoid having to make a second trip to hospital. Many families declined to return to hospital for vaccination at a separate visit, and were thus left unvaccinated and at risk of infection.
- The vaccine to be administered in this study is part of the routine UK National Immunisation Schedule. The study allows children to participate in this programme in a safe environment, utilising a vaccine delivery route (intranasal) which minimises discomfort to the child.
- The proposed consent process has been trialled successfully in the SNIFFLE-2 and -3 studies, with positive feedback from both eligible young people and their families.

Following discussion with the Research Ethics Committee, it has been agreed that **in participants under 16 years at the time of consent** and vaccination, but who will turn 16 years of age prior to the 4 week follow-up assessment, the participant does not need to be formally consented as it can be assumed that in voluntarily answering the questionnaire, the participant provides consent.

However, for participants at the Royal Brompton site undergoing further assessment at the 4 week follow-up (as outlined in section 8.3), formal consent will need to be taken from the young person prior to the assessments being performed.

